APPENDIX I: CTEP AND CTSU REGISTRATION PROCEDURES

INVESTIGATOR AND RESEARCH ASSOCIATE REGISTRATION WITH CTEP

Food and Drug Administration (FDA) regulations and National Cancer Institute (NCI) policy require all individuals contributing to NCI-sponsored trials to register and to renew their registration annually. To register, all individuals must obtain a Cancer Therapy Evaluation Program (CTEP) Identity and Access Management (IAM) account at <https://ctepcore.nci.nih.gov/iam>. In addition, persons with a registration type of Investigator (IVR), Non-Physician Investigator (NPIVR), or Associate Plus (AP) must complete their annual registration using CTEP’s web-based Registration and Credential Repository (RCR) at <https://ctepcore.nci.nih.gov/rcr>.

RCR utilizes five person registration types.

- IVR — MD, DO, or international equivalent;
- NPIVR — advanced practice providers (e.g., NP or PA) or graduate level researchers (e.g., PhD);
- AP — clinical site staff (e.g., RN or CRA) with data entry access to CTSU applications such as the Roster Update Management System (RUMS), OPEN, Rave, acting as a primary site contact, or with consenting privileges;
- Associate (A) — other clinical site staff involved in the conduct of NCI-sponsored trials; and
- Associate Basic (AB) — individuals (e.g., pharmaceutical company employees) with limited access to NCI-supported systems.

RCR requires the following registration documents:

Documentation Required	IVR	NPIVR	AP	A	AB
FDA Form 1572	✓	✓			
Financial Disclosure Form	✓	✓	✓		
NCI Biosketch (education, training, employment, license, and certification)	✓	✓	✓		
GCP training	✓	✓	✓		
Agent Shipment Form (if applicable)	✓				
CV (optional)	✓	✓	✓		

An active CTEP-IAM user account and appropriate RCR registration is required to access all CTEP and Cancer Trials Support Unit (CTSU) websites and applications. In addition, IVRs and NPIVRs must list all clinical practice sites and Institutional Review Boards (IRBs) covering their practice sites on the FDA Form 1572 in RCR to allow the following:

- Addition to a site roster;
- Assign the treating, credit, consenting, or drug shipment (IVR only) tasks in OPEN;
- Act as the site-protocol Principal Investigator (PI) on the IRB approval; and
- Assign the Clinical Investigator (CI) role on the Delegation of Tasks Log (DTL).

In addition, all investigators acting as the Site-Protocol PI (investigator listed on the IRB approval), consenting/treating/drug shipment investigator in OPEN, or as the CI on the DTL must be rostered at the enrolling site with a participating organization.

Additional information is located on the CTEP website at <https://ctep.cancer.gov/investigatorResources/default.htm>. For questions, please contact the RCR *Help Desk* by email at [contact].

CTSU REGISTRATION PROCEDURES

This study is supported by the NCI Cancer Trials Support Unit (CTSU).

Downloading Site Registration Documents:

Download the site registration forms from the protocol-specific page located on the CTSU members' website. Permission to view and download this protocol and its supporting documents is restricted based on person and site roster assignment. To participate, the institution and its associated investigators and staff must be associated with the LPO or a Protocol Organization (PO) on the protocol. One way to search for a protocol is listed below.

- Log in to the CTSU members' website (<https://www.ctsu.org>) using your CTEP-IAM username and password;
- Click on *Protocols* in the upper left of the screen
 - Enter the protocol number in the search field at the top of the protocol tree; or
 - Click on the By Lead Organization folder to expand, then select *COG*, and protocol number (*insert study number*).
- Click on *Documents*, select *Site Registration*, and download and complete the forms provided. (Note: For sites under the CIRB, IRB data will load automatically to the CTSU.)

Protocol-Specific Requirements For Site Registration:

- IRB approval (For sites not participating via the NCI CIRB; local IRB documentation, an IRB-signed CTSU IRB Certification Form, Protocol of Human Subjects Assurance Identification/IRB Certification/Declaration of Exemption Form, or combination is accepted)

Submitting Regulatory Documents:

Submit required forms and documents to the CTSU Regulatory Office using the Regulatory Submission Portal on the CTSU website.

To access the Regulatory Submission Portal log in to the CTSU members' website, go to the Regulatory section and select Regulatory Submission.

Institutions with patients waiting that are unable to use the Regulatory Submission Portal should alert the CTSU Regulatory Office immediately at [name] in order to receive further instruction and support.

Checking Your Site's Registration Status

Site registration status may be verified on the CTSU members' website.

- Click on *Regulatory* at the top of the screen;
- Click on *Site Registration*; and
- Enter the site's 5-character CTEP Institution Code and click on Go.
 - Additional filters are available to sort by Protocol, Registration Status, Protocol Status, and/or IRB Type.

Note: The status shown only reflects institutional compliance with site registration requirements as outlined within the protocol. It does not reflect compliance with protocol requirements for individuals participating on the protocol or the enrolling investigator's status with NCI or their affiliated networks.

Data Submission / Data Reporting

Medidata Rave is a clinical data management system being used for data collection for this trial/study. Access to the trial in Rave is controlled through the CTEP-IAM system and role assignments.

Requirements to access Rave via iMedidata:

- A valid CTEP-IAM account; and
- Assigned a Rave role on the LPO or PO roster at the enrolling site of: Rave CRA, Rave Read Only, Rave CRA (LabAdmin), Rave SLA, or Rave Investigator.

Rave role requirements:

- Rave CRA or Rave CRA (Lab Admin) role must have a minimum of an Associate Plus (AP) registration type;
- Rave Investigator role must be registered as a Non-Physician Investigator (NPIVR) or Investigator (IVR); and
- Rave Read Only role must have at a minimum an Associates (A) registration type.

Refer to <https://ctep.cancer.gov/investigatorResources/default.htm> for registration types and documentation required.

Upon initial site registration approval for the study in Regulatory Support System (RSS), all persons with Rave roles assigned on the appropriate roster will be sent a study invitation e-mail from iMedidata. To accept the invitation, site staff must log in to the Select Login (<https://login.imedidata.com/selectlogin>) using their CTEP-IAM username and password and click on the *accept* link in the upper right-corner of the iMedidata page. Site staff will not be able to access the study in Rave until all required Medidata and study specific trainings are completed. Trainings will be in the form of electronic learnings (eLearnings) and can be accessed by clicking on the link in the upper right pane of the iMedidata screen. If an eLearning is required and has not yet been taken, the link to the eLearning will appear under the study name in iMedidata instead of the *Rave EDC* link; once the successful completion of the eLearning has been recorded, access to the study in Rave will be granted, and a *Rave EDC* link will display under the study name.

Site staff that have not previously activated their iMedidata/Rave account at the time of initial site registration approval for the study in RSS will receive a separate invitation from iMedidata to activate their account. Account activation instructions are located on the CTSU website in the Data Management section under the Rave resource materials (Medidata Account Activation and Study Invitation Acceptance). Additional information on iMedidata/Rave is available on the CTSU members' website in the Data Management > Rave section at www.ctsu.org/RAVE/ or by contacting the CTSU Help Desk at [name] or by e-mail at [contact].

APPENDIX II: DOSING NOMOGRAM

Consistent with dose levels defined in the pediatric solid tumor study, trametinib dosing will be weight based. The drug is supplied in tablet form or in or solution form, with dosing nomogram for tablet formulation below. **The maximum dose is 2 mg per day.**

Note: If switching from trametinib solution to trametinib tablets or vice versa in patients requiring dose reduction, match up the patient's starting dose to ensure the proper dose reduction is being made.

Dose Level: 0.025 mg/kg/dose PO once daily (age ≥ 6 years)						
Subject Weight: ≥ 35 kg						
Formulation: Trametinib Tablets 0.5 and 2 mg						
Actual Weight*(kg)	Dose (mg)	Number of 0.5 mg tablets	Number of 2 mg tablets	Dose Reduction (mg)	Number of 0.5 mg tablets	Number of 2 mg tablets
35 – 50	1 mg	2	0	Oral solution only 0.75 mg (15 mL)		
50.1 – 70	1.5 mg	3	0	1 mg	2	0
≥ 70.1	2 mg	0	1	1.5 mg	3	0

*weight measured within 7 days of the start of the cycle

Dose Level: 0.032 mg/kg/dose PO once daily (age 1 month to < 6 years)						
Subject Weight: ≥ 26.6 kg						
Formulation: Trametinib Tablets 0.5 and 2 mg						
Actual Weight*(kg)	Dose (mg)	Number of 0.5 mg tablets	Number of 2 mg tablets	Dose Reduction (mg)	Number of 0.5 mg tablets	Number of 2 mg tablets
26.6 – 39	1 mg	2	0	Oral solution only 0.75 mg (15 mL)		
39.1 – 54.6	1.5 mg	3	0	1 mg	2	0
≥54.7	2 mg	0	1	1.5 mg	3	0

*weight measured within 7 days of the start of the cycle

APPENDIX III: RESPONSE CRITERIA FOR PATIENTS WITH JMML

Table 1: Variables for evaluation of response to therapy in JMML

Variables for Response	Definition of response			Definition of disease progression or relapse (applicable to all patients)	
	Assessment of CR and PR is feasible if the following are present before therapy	Requirement for CR for each variable (vCR)	Requirement for PR for each variable (vPR)	Requirement for PD for each variable (vPD)	
Clinical variables	1) WBC count	>20 × 10 ⁹ /L	3.0 – 15.0 × 10 ⁹ /L	Decreased by ≥50% over pretreatment but still >15 × 10 ⁹ /L	Increase by ≥50% and ≥20 × 10 ⁹ /L
	2) Myeloid and erythroid precursors and blasts in PB*	≥ 5%	0-1%	Decreased by ≥50% over pretreatment but still ≥ 2%	Increase from the baseline: < 5%: ≥ 50% increase and ≥ 5% ≥ 5%: ≥ 50% increase of total % of myeloid and erythroid precursors and blasts
	3) Platelet count	<100 × 10 ⁹ /L	>100 × 10 ⁹ /L	For patients starting with ≥ 20 × 10 ⁹ /L platelets: absolute increase of ≥ 30 × 10 ⁹ /L For patients starting with < 20 × 10 ⁹ /L platelets: increase by ≥ 100% and > 20 × 10 ⁹ /L	Development of transfusion dependency or if patients have the baseline of the platelet count of ≥30 × 10 ⁹ /L, decrease by ≥50% and <100 × 10 ⁹ /L
	4) BM blasts	≥5%	<5%	Decreased by ≥50% over pretreatment but still ≥5%	Increase from base line; < 5%: ≥ 50% increase and ≥ 5% ≥ 5%: ≥ 50% increase of BM blasts
	5) Spleen size				
	a) Clinical evaluation or	≥2 cm under the costal margin	No splenomegaly	50% decrease by cm under the costal margin	Increase by ≥100% if baseline <4cm from under the costa margin ≥50% if baseline 5-10cm >30% if baseline >10 cm
b) Sonography	Length of spleen ≥ 150% of upper limit of normal range	No splenomegaly	>25% decrease by length, but still splenomegaly	Increase by ≥25% of length	
6) Extramedullary disease#	Extramedullary leukemic infiltration	No evidence of extramedullary leukemic infiltration in any organ	-	Worsening or new lesions of extramedullary leukemic infiltration	
7) Cytogenetic response	Somatic cytogenetic abnormality detected	Normal karyotype	-	Reappearance or additional acquirement of cytogenetic abnormalities	
8) Molecular response	Somatic genetic anomalies detected**	Absence of somatic genetic anomalies	-	Reappearance or additional acquirement of JMML-specific somatic gene abnormalities	
9) Chimerism response (only for patients after HSCT)	>15% autologous cells after allo-HSCT	Complete donor chimerism	-	50% increase and >5% increase of autologous cells and >5%	

CR: complete response, PR: partial response, PD: progressive disease, WBC: white blood cell, PB: peripheral blood, BM: bone marrow

*Myeloid precursors include promyelocytes, myelocytes, and metamyelocytes. The myeloid and erythroid precursors and blasts in PB are given as % of the total nucleated cells in PB (WBC including erythroblasts).

**in *NF-1*, *PTPN11*, *NRAS*, *KRAS*, *RRAS2*, or *CBL*, thus the mutation are thought to be initiating. In patients with germ-line *NF-1*, *PTPN11* or *CBL* mutation, only acquired mutations can be evaluated for response and relapse after therapy. The germ-line mutation remains even if patients achieved complete molecular response. The molecular response will be determined using the “JMML Mutant Allele Burden” assay.

Criteria for progression including WBC, platelet count and spleen size cannot be used in the setting of an active infection.

#Extramedullary disease includes infiltration of skin, lung, and very rarely cranial nerves or central nervous system.

Table 2: Definition of response following therapy other than HSCT in JMML

Clinical remission status: parameter 1-6 of table 1		Genetic remission status: parameter 7-9 of table 1	
Clinical complete remission (cCR)	Patient fulfills the criteria of CR of all applicable clinical variables 1-6 of table 1 The response parameters must be maintained for at least 4 weeks.	Genetic complete remission (gCR)	Defined if the patient shows a normal karyotype and absence of acquired mutations in PTPN11 , NF-1 , NRAS , KRAS , or CBL .
Clinical partial remission (cPR)	Defined if the patient does not fulfill the criteria of cCR, but vPR was achieved in at least one of clinical variables (1 – 6) and none of clinical variables showed vPD.	-	-
Clinical stable disease (cSD)	Defined if the patient does not fulfill the criteria of cCR and cPR, but none of the parameter showed vPD.	Genetic stable disease (gSD)	Defined if the patient does not fulfill the criteria of gCR, but none of the genetic parameters (7-9) showed vPD.
Clinical progressive disease (cPD)	Defined if any of the parameters 1-6 showed vPD.	Genetic progressive disease (gPD)	Defined if any of the parameters 7-9 showed vPD.
Clinical relapse (cRel)	Defined if any of the parameters 1 - 6 showed vPD after the achievement of cCR or cPR.	Genetic relapse (gRel)	Reappearance of an abnormal karyotype and/or mutation of genes related with JMML if previously undetected, and/or (only for patients after HSCT) increase in recipient chimerism with at least 10% of autologous cells and >50% increase above the base line.

**In patients with germ-line *NF-1*, *PTPN11* or *CBL* mutation, the germ-line mutation remains even if patients achieved a genetic complete remission.

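### Appendix III has no palpation-based spleen progression rule for a baseline of 4 to under 5 cm, so marked spleen growth in that band need not count as progression

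*Combined protocol and SAP*

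**What the plan says.** Appendix III, Table 1 gives two ways to judge spleen progression (vPD), joined as alternatives.

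- **5a, clinical evaluation, in cm below the costal margin:** "Increase by ≥100% if baseline <4cm from under the costa margin", then "≥50% if baseline 5-10cm >30% if baseline >10 cm".
- **5b, sonography:** "Increase by ≥25% of length", with no baseline bands.

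The column that holds these rules is headed "Definition of disease progression or relapse (applicable to all patients" (the closing bracket is omitted here). Spleen response by palpation can be assessed from a baseline of "≥2 cm under the costal margin", so a 4 to under 5 cm spleen is in scope.

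Table 2 turns the variables into a clinical status. Clinical partial remission (cPR) requires that "vPR was achieved in at least one of clinical variables (1 – 6) and none of clinical variables showed vPD". Clinical progression (cPD) is "Defined if any of the parameters 1-6 showed vPD". Section 10.2 crosses clinical with genetic status: cPR with stable genetics (gSD) is an overall PR, and cPD is PD in every genetic row. Section 9.3 counts a patient as a responder if PR or CR is reached before an overall PD.

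**The concern.** The bands stop below 4 cm and start again at 5 cm. For a baseline in between, no amount of growth found by palpation can produce vPD. Because cPR needs one improved variable and the absence of any vPD, a missing progression rule can only push classification towards response, and this is the primary endpoint. Sites that notice the gap would have to improvise, and could do so differently.

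PD has other uses. It ends the duration of response (Section 9.3), bars the next cycle (Section 4.1.3) and is a reason for removal from protocol therapy (Section 8.1). All of these inherit the gap.

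**Working it through.** **1. The bands, read literally (Table 1, variable 5a).**

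| Baseline by palpation | Growth needed for vPD | Example |
|---|---|---|
| below 4 cm | ≥100% | 3.9 cm: vPD at 2 × 3.9 = 7.8 cm |
| 4 to under 5 cm | none stated | 4.0, 4.5, 4.9 cm: no vPD at +50%, +100% or +200% |
| 5-10 cm | ≥50% | 5 cm: vPD at 1.5 × 5 = 7.5 cm |
| above 10 cm | >30% | 10.5 cm: vPD above 1.3 × 10.5 = 13.65 cm |

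Recording in whole centimetres does not help: 4 cm is neither below 4 nor within 5-10.

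**2. A worked patient.**
- Spleen: 4.5 cm to 12 cm, (12 − 4.5)/4.5 = 1.67, or +167%. The lower neighbour's threshold would give vPD at 2 × 4.5 = 9.0 cm, the upper neighbour's at 1.5 × 4.5 = 6.75 cm. Twelve centimetres exceeds both.
- WBC: 60 to 28 × 10⁹/L. The baseline exceeds 20, so the variable is assessable; (60 − 28)/60 = 53% is at least a 50% fall; 28 is still above 15. This is vPR.
- No other variable shows vPD, and genetic status is gSD.
- As printed: one vPR and no vPD give cPR; cPR with gSD gives an overall PR.
- Under either neighbouring threshold: vPD gives cPD, and cPD gives PD.

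A second route exists: complete genetic remission with clinical stable disease is an overall CR in Section 10.2, and stable disease also depends on there being no vPD. Clinical complete remission is not reachable this way, because the enlarged spleen is an applicable variable that has not reached CR.

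**3. Timing.** Under Section 9.3 the first qualifying response counts if it precedes PD. If the spleen grows before or together with the WBC response, the gap decides whether the patient is a responder. If it grows afterwards, the patient is a responder with or without the gap, and what is lost is the end of the duration of response.

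**4. What one patient is worth (Section 9.2).** With X the stage 1 responses, Y the stage 2 responses and b(10, x, p) the binomial probability of x responses in 10:

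P(effective) = Σ over x = 1 to 10 of b(10, x, p) × P(Y ≥ max(0, 3 − x)).

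- At p = 5%: early stopping 0.95¹⁰ = 0.5987 (plan 0.599); P(effective) 0.0686 (plan 0.069); expected size 10 + 10 × (1 − 0.5987) = 14.01 (plan 14.01).
- At p = 25%: P(effective) 0.8820 (plan 0.882).

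The plan's figures reproduce and are not in dispute. One responder is 1/20 = 5 percentage points, one third of the 3 responses needed, and enough alone to open stage 2.

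**5. Illustration on assumed inputs.** Let s be the share of patients in the band and m the share of non-responders there who are scored PR only because of the gap. The apparent rate at a true 5% is 0.05 + 0.95 × s × m.
- s = 5%, m = 5%: 0.05 + 0.95 × 0.0025 = 0.0524; P(effective) 0.077.
- s = 20%, m = 25%: 0.05 + 0.95 × 0.05 = 0.0975; P(effective) 0.285.

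The documents support neither value. The upper end needs one patient in five inside a 1 cm band and a quarter of the non-responders among them converted.

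**The case against.** A reader might infer that these patients have no spleen progression rule at all. That goes too far. Under 5b a length increase of at least 25% is vPD at any baseline, so a patient followed by sonography is covered. But 5b is only an alternative, and the required observations in Sections 4.2.2, 4.3.2 and 4.4.2 list physical examination and no spleen sonography. Follow-up by palpation alone is permitted, and for it the gap stands.

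A reader might also infer that any patient in the band whose WBC halves becomes a PR. The table does not say so. A fall from 25 to 12.5 × 10⁹/L lands in the CR range for that variable and is not vPR; exact halving gives vPR only from a baseline above 2 × 15 = 30. Stable genetics and no vPD elsewhere are needed too, since genetic progression makes the overall response PD.

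Nor do the documents show that the trial's error rate is materially inflated. The band is narrow, vPD in another variable still gives PD, and the growth must not come after the response. The illustration shows sensitivity, not a likely effect.

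Finally, Section 10.2 attributes the criteria to an international consensus panel. Whether the gap was inherited or arose in transcription cannot be told from these documents. Either way, it is in the rule this trial will apply.

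**Conclusion.** The gap is real but minor. Variable 5a, applied literally by palpation, cannot register progression from a baseline of 4 to under 5 cm, and a patient whose growth exceeds both neighbouring thresholds can be classified as a responder. It looks unintended: the column is meant for all patients, and the blast and precursor rules in variables 2 and 4 split at 5% with nothing left out.

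The conclusion rests on palpation being the measure used, on an improvement in another clinical variable (or complete genetic remission), on no vPD elsewhere, and, for response status, on growth before or with the first response. The number of patients affected is unknown and may well be zero. The point still merits correction because a single classification can decide either stage.

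**What to change.** Revise the 5a cell so that the bands are contiguous and every baseline falls in exactly one. The documents do not show whether the ≥100% or the ≥50% threshold was meant for 4 to under 5 cm. The choice matters for growth between the two: at a 4.5 cm baseline, between 6.75 and 9.0 cm. Because PD also governs continuation of therapy, the sponsor should reconcile the bands and record the reason; this review does not propose a cut-off.

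Add a sentence fixing 5a or 5b as the spleen measure for each patient at baseline. Apply the completed rule to all patients, including those already enrolled, before responses are finally classified.

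The cost is one table cell and one sentence. Sample size, decision rule and visit schedule do not change.

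### The genetic complete remission cell in Appendix III Table 2 omits RRAS2 and Table 1's baseline condition, so a clinically stable patient can be scored either CR or SD

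*Combined protocol and SAP*

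**What the plan says.** **Table 1 of Appendix III** sets a baseline condition for every response variable. Its column is headed "Assessment of CR and PR is feasible if the following are present before therapy". For variable 7 this is a somatic cytogenetic abnormality, and for variable 8 a somatic genetic anomaly. The requirement for molecular CR is "Absence of somatic genetic anomalies". The footnote to variable 8 lists NF-1, PTPN11, NRAS, KRAS, RRAS2 and CBL, on the ground that "thus the mutation are thought to be initiating". It adds that in germ-line carriers "only acquired mutations can be evaluated for response and relapse after therapy", and that the JMML mutant allele burden assay determines molecular response. Section 7.3 lists RRAS2 among the genes that assay sequences.

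**Table 2 of Appendix III** defines the composite categories. The genetic column is headed "Genetic remission status: parameter 7-9 of table 1". Its gCR cell reads "Defined if the patient shows a normal karyotype and absence of acquired mutations in" PTPN11, NF-1, NRAS, KRAS or CBL. The clinical CR cell beside it is worded differently: "Patient fulfills the criteria of CR of all applicable clinical variables 1-6 of table 1". Genetic stable disease (gSD) is the residual category: "Defined if the patient does not fulfill the criteria of gCR, but none of the genetic parameters (7-9) showed vPD".

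**Section 10.2** crosses the two columns. gCR with clinical stable disease (cSD) is an overall CR; gSD with cSD is SD. **Section 9.3** counts a best response of PR or CR before PD as a response. **Section 9.4** makes every patient who receives one dose evaluable, with no requirement for a genetic lesion.

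**The concern.** The gCR cell describes a state, not a change. Nothing in it asks whether there was a listed lesion to clear, and it is silent on one gene that Table 1 treats as an initiating lesion. Two kinds of patient with a normal karyotype can therefore satisfy it with no change in their disease: one whose only acquired mutation is in RRAS2 and persists, and one with no acquired lesion at entry.

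Both can be enrolled. Section 3.2.2 allows diagnosis on two Category 3 features with no Category 2 feature, and it accepts a clinical diagnosis of NF1. Section 3.2.3.1 allows persistent disease to be shown by clinical symptoms.

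At stake are the primary response rate, with its two-stage decision rule, and the CR rate of Aim 1.2.4. The rule stops at 0 of 10 and declares the agent effective at 3 of 20, so a single reclassified patient carries weight. In an open-label single-arm trial, the choice between the two texts should not be left to case-by-case review.

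**Working it through.** **Step 1. Classify the same patient under each text** (clinically stable, normal karyotype throughout).

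| Patient | Table 2 cell as written | Read with Table 1 |
|---|---|---|
| Persisting RRAS2-only mutation | gCR (RRAS2 not listed) → CR → responder | variable 8 not in CR → gSD → SD → non-responder |
| No acquired lesion at entry | gCR (nothing to find) → CR → responder | CR not assessable → residual gSD → SD → non-responder |

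With clinical progression both patients are PD under either text. With cPR or cCR both are responders under either text, but CR as written and PR when read with Table 1. The primary endpoint therefore changes only for cSD patients; the CR rate changes for cSD, cPR and cCR patients.

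**Step 2. Reproduce the plan's figures** (Section 9.2: stop at 0/10; effective at 3 or more of 20).

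P(effective) = Σ over x from 1 to 10 of P(X₁ = x) · P(X₂ ≥ 3 − x), with X₁ and X₂ each Bin(10, p).

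- At p = 0.05: 0.3151 × 0.0861 + 0.0746 × 0.4013 + 0.0115 = 0.0686 (plan: 0.069).
- Early stopping: 0.95¹⁰ = 0.599 (plan: 59.9%).
- At p = 0.25: 0.8820 (plan: 0.882).

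**Step 3. Put exactly one automatic responder among the 20**, the other 19 responding at 5%.

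- *In stage 1.* Stage 1 is passed with certainty, instead of with probability 1 − 0.599 = 0.401. Two more responses are needed from 19: P(Bin(19, 0.05) ≥ 2) = 1 − 0.3774 − 0.3774 = 0.245.
- *In stage 2.* At least one of the first 10 must respond, and at least two of the 19 overall. One response in stage 1 contributes 0.3151 × (1 − 0.95⁹) = 0.3151 × 0.3698 = 0.1165. Two or more in stage 1 contribute 0.0861. The sum is 0.203.
- *CR rate.* 1/20 = 5 percentage points.

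**Step 4. Show the range over an assumed share.** Let u be the share of enrolled patients affected and s the share of those with a non-progressing assessment. The documents give neither. The scored rate at a true 5% is 0.05 + 0.95·u·s.

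| u (assumed) | P(at least one in 20) | P(effective), s = 25% to 100% |
|---|---|---|
| 1% | 1 − 0.99²⁰ = 0.18 | 0.077 to 0.103 |
| 5% | 1 − 0.95²⁰ = 0.64 | 0.112 to 0.285 |

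At u = 0 the figure stays at 0.069.

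**The case against.** The best reply is that the documents largely point to Table 1. The genetic column's own heading refers to Table 1's parameters 7 to 9. Section 10.2 sends the reader to the Appendix III tables together, and Section 4.4.2 names Tables 1 and 2. The footnote ties molecular response to an assay that includes RRAS2, so the shorter gene list looks like an editing lag. The cPR cell does not repeat the baseline condition either, so its absence from the gCR cell is weak evidence that it was dropped. All of this stands as evidence of intent. It does not settle the matter, because the gCR cell states a complete rule with its own gene list and no text says which prevails.

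Three stronger readings are tempting and are not supported:

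- *That the plan intends unchanged disease to count as CR, or that its type I error really exceeds 0.069.* The design figures reproduce exactly. They move only if the cell is applied literally and an affected patient is enrolled.
- *That about 5% of patients are affected, because Section 2.1.1 puts Ras-pathway mutations at 95% of JMML.* That figure describes JMML in general. Some patients without such a mutation may have an abnormal karyotype, and no RRAS2-only share is given. It shows plausibility only.
- *That every germ-line NF1 or CBL carrier is automatically gCR.* Section 2.1.1 describes somatic loss of heterozygosity in such disease, so a germ-line diagnosis does not by itself mean there is no acquired lesion.

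Section 10.2 attributes the criteria to an international consensus panel. Whether the cell follows that source cannot be judged from these documents, and the point does not depend on it.

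**Conclusion.** The inconsistency is real and reaches the primary endpoint. The gCR cell lacks RRAS2 and the baseline condition, and the documents state no precedence between it and Table 1. A clinically stable patient of either kind is a complete responder under one text and a non-responder under the other.

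The size is conditional. With no such patient enrolled there is no effect. With exactly one, and the literal text applied, the chance of a false declaration of activity at a true 5% rate is 0.245 or 0.203 instead of 0.069, depending on the stage. The wider range in the working rests wholly on assumed values of u and s, and its upper ends need every affected patient to have a non-progressing assessment. For the patient with no baseline lesion, SD follows from the residual wording of gSD. One could instead call that patient genetically not assessable, but Section 10.2 has no such row. This should be settled before responses are classified.

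**What to change.** In the Table 2 gCR cell:

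1. Add RRAS2 to the gene list.
2. Add one sentence: *gCR can be assigned only if a Table 1 variable 7 or 8 abnormality (a somatic cytogenetic abnormality, or an acquired mutation in a listed gene) was documented before therapy; otherwise, absent vPD, the patient is gSD.*

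Leave the rest of the cell alone. Copying the clinical CR cell's wording would not work: a patient with no applicable genetic variable would still qualify by default, and its four-week maintenance rule might come along. Requiring CR on all of variables 7 to 9 would add a donor-chimerism requirement that the cell does not now contain and that the scheduled observations do not cover. The Section 10.2 grid needs no new row.

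**Cost.** One gene name and one sentence. No new tests are needed, because the baseline panel and marrow cytogenetics are already required in Section 4.2.2. The observed response rate may fall slightly. A patient with no baseline genetic lesion who reaches cCR becomes PR rather than CR, so the Aim 1.2.4 CR rate should also be reported among patients with a baseline genetic lesion. Such patients can still respond through the gSD row. Even if they never did, power at a true 25% rate would be 0.877 with u = 1% (p = 0.25 × 0.99 = 0.2475) and 0.858 with u = 5% (p = 0.25 × 0.95 = 0.2375), against 0.882.
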